### 3. **Withdrawing Your Dose From the Vial**

- a. Cleanse the rubber stopper of the vial containing the Interferon solution with an alcohol pad and allow to air dry.
- b. Open syringe package and needle package (if separate) and attach or tighten needle by twisting until tight. Pull back the plunger to the mark that represents your dose (i.e., 3 mIU/0.5 ml, top of plunger should rest at the 0.5 ml mark). This fills the syringe with air in a volume equal to the volume of your dose.
- c. Uncap the needle and push it through the stopper, at least half-way into the vial. Now pick up the vial (with syringe/needle in it) with your left hand and turn it upside down, holding it at eye-level, about 12 inches from your face. You should now have the vial in one hand and your other hand free to manipulate the syringe. (Note: Left-handed persons should have the vial in their right hand, so that they can manipulate the syringe with their left hand.)
- d. Inject air from the syringe into the vial slowly, and then withdraw the plunger. The syringe will gradually fill with drug solution. Repeat this procedure until only solution is in the syringe, solidly, to the mark that indicates your dose. Withdraw needle and recap it.

### 4. **Administration**

- a. Thoroughly clean the area to be injected with an alcohol pad. Areas appropriate for this type of injection have been shown to you. A new site should be used for each injection whenever possible.
- b. As demonstrated, pinch 1½ to 2 inches of loose skin from the site to be injected.
- c. Uncap the needle, and insert the needle approximately ¼ inch into the skin and push the syringe plunger in all the way, thereby giving the dose of Interferon.
- d. Remove needle and wipe injection site with a new alcohol pad, but do not massage the area to any great extent.
- e. Needles are not to be recapped. Used needles and used syringes should be disposed of in the proper disposal container provided by your pharmacy and returned to the clinic pharmacy for disposal. If the Interferon vial contains more than one dose, write the date on the label. It is usable for 30 days. INTRON A injection vials should be stored in the refrigerator between 2° and 8° C (36° and 46°F), not in the freezer.
- f. If a drug administration diary has been provided, remember to complete it after each dose. Enter the date and time of day given, along with any notable side effects that you may have experienced since previous dose was given. Also record vial strength and dose volume at each entry.

**A Phase III Randomized Study of Adjuvant Ipilimumab Anti-CTLA4 Therapy Versus High Dose Interferon a-2b for Resected High risk Melanoma**

**Appendix XI**

**TNM Staging for Melanoma**

Table 1. TNM Staging Categories for Cutaneous Melanoma		
Classification	Thickness (mm)	Ulceration Status/Mitoses
T		
Tis	NA	NA
T1	≤ 1.00	a: Without ulceration and mitosis < 1/mm  b: With ulceration or mitoses ≥ 1/mm 
T2	1.01-2.00	a. without ulceration b. with ulceration
T3	2.01-4.00	a: without ulceration b: with ulceration
T4	> 4.00	a. without ulceration b: with ulceration
N	No. of Metastatic Nodes	Nodal Metastatic Burden
N0	0	NA
N1	1	a: Micrometastasis* b: Macrometastasis †
N2	2-3	a: Micrometastasis* b: Macrometastasis † c: In transit metastases/satellites without metastatic nodes
N3	4+ metastatic nodes, or matted nodes, or in transit metastases/ Satellites with metastatic nodes	
M	Site	Serum LDH
M0	No distant metastases	NA
M1a	Distant skin, subcutaneous, or nodal metastases	Normal
M1b	Lung metastases	Normal
M1c	All other visceral metastases Any distant metastasis	Normal Elevated
Abbreviations: NA, not applicable; LDH, lactate dehydrogenase, *Micrometastases are diagnosed after sentinel lymph node biopsy. †Macrometastases are defined as clinically detectable nodal metastases confirmed pathologically.		

Table 2. Anatomic Stage Groupings for Cutaneous Melanoma								
	Clinical Staging*				Pathological Staging †			
	T	N	M		T	N	M	
0	Tis	N0	M0	0	Tis	N0	M0	
IA	T1a	N0	M0	IA	T1a	N0	M0	
IB	T1b	N0	M0	IB	T1b	N0	M0	
	T2a	N0	M0		T2a	N0	M0	
IIA	T2b	N0	M0	IIA	T2b	N0	M0	
	T3a	N0	M0		T3a	N0	M0	
IIB	T3b	N0	M0	IIB	T3b	N0	M0	
	T4a	N0	M0		T4a	N0	M0	
IIC	T4b	N0	M0	IIC	T4b	N0	M0	
III	Any T	N> N0	M0	IIIA	T1-4a	N1a	M0	
				IIIB	T1-4a	N2a	M0	
					T1-4b	N1a	M0	
					T1-4b	N2a	M0	
					T1-4a	N1b	M0	
					T1-4a	N2b	M0	
					T1-4a	N2c	M0	
				IIIC	T1-4b	N1b	M0	
					T1-4b	N2b	M0	
					T1-4b	N2c	M0	
					Any T	N3	M0	
					IV	Any T	Any N	M1

\*Clinical staging includes microstaging of the primary melanoma and clinical/radiologic evaluation for metastases. By convention, it should be used after complete excision of the primary melanoma with clinical assessment for regional and distant metastases.

[figure not shown]
†Pathologic staging includes microstaging of the primary melanoma and pathologic information about the regional lymph nodes after partial (ie, sentinel node biopsy) or complete lymphadenectomy. Pathologic stage 0 or stage IA patients are the exception; they do not require pathologic evaluation of their lymph nodes.

**Appendix XII**

**General Recommendations for immune-related Adverse Events (irAEs)**

Rev. 2/14

\* A complete list of irAEs can be found in Section 5.5.1.3  
\*\* Based on clinical experience to date, systemic steroids for treatment of irAEs do not appear to impact the development or maintenance of ipilimumab clinical activity in advanced melanoma.

## A Phase III Randomized Study of Adjuvant Ipilimumab Anti-CTLA4 Therapy Versus High Dose Interferon a-2b for Resected High risk Melanoma

### Appendix XIII

#### Suggested Work-up and Treatment for Immune-Related Adverse Events (irAEs)

An IRAE is defined as an adverse event of unknown etiology, associated with drug exposure and is consistent with an immune phenomenon. Efforts should be made to rule out neoplastic, infectious, metabolic, toxin or other etiologic causes prior to labeling an adverse event a non-dermatologic, immune-mediated event. Serological, immunological, and histological (biopsy) data should be used to support the diagnosis of an immune-mediated toxicity. Documentation of test results should be included in the patient's medical record. Effective Amendment #7, the dose delay and discontinuation criteria have been made stricter on Arms A or D (ipilimumab 10 mg/kg) than on Arms C or F (ipilimumab 3 mg/kg) due to a higher incidence of severe toxicities observed on Arms A and D compared to Arms C and F.

Gastrointestinal (diarrhea) and skin (rash)-related toxicities have been the most common IRAEs noted in prior studies with ipilimumab. Suggested work-up procedures for suspected IRAEs of the gastrointestinal tract, liver, skin, eye, pituitary, and adrenal gland are listed below. When symptomatic therapy is inadequate or inappropriate, an IRAE should be treated with steroids followed by a slow taper.

**Gastrointestinal Tract:** Diarrhea (defined as either first watery stool, or increase in frequency 50% above baseline with urgency or nocturnal bowel movement, or bloody stool) should be further evaluated and infectious or alternate etiologies ruled out. Patients should be advised to inform the investigator if any diarrhea occurs, even if it is mild. An algorithm for working up patients with diarrhea or suspected colitis is provided in [Appendix XIV](#).

If the event is of significant duration or magnitude or is associated with signs of systemic inflammation or acute phase reactants (e.g., increased CRP or platelet count; or bandemia), it is recommended that sigmoidoscopy (or colonoscopy, if appropriate) with colonic biopsy with 3 to 5 specimens for standard paraffin block be performed. If possible, 1 to 2 biopsy specimens should be snap frozen and stored. All patients with confirmed colitis should also have an ophthalmological examination, including a slit-lamp exam, to rule out uveitis. Tests should also be performed for WBCs and for stool calprotectin.

Patients with colitis should discontinue any non-steroidal anti-inflammatory medications or any other medications known to exacerbate colitis symptoms. Investigators should use their clinical judgment as to whether corticosteroids are necessary to treat colitis associated with ipilimumab therapy and as to what dose should be used. As guidance prior experience suggests that colitis manifested as  $\geq$  Grade 3 diarrhea requires corticosteroid treatment and possibly other immunosuppressants as noted in the E1609 study protocol (Sections [5.5.1.3](#), [5.5.1.5](#)) and [Appendix XIV](#).

**Liver:** Elevation of LFTs from baseline should instigate an investigation into the underlying etiology for suspected IRAEs, in accordance with Sections [5.5.1.3](#), [5.5.1.5](#) and [Appendix XV](#). Neoplastic, concurrent medications, viral hepatitis, and toxic etiologies should be considered and addressed, as appropriate. Imaging of the liver, gall bladder, and bile duct should be performed to rule out neoplastic or other causes for the increased LFTs. An ANA, pANCA, and anti-smooth muscle antibody test should be performed if an autoimmune etiology is considered. Consultation with a hepatologist is appropriate for a suspected liver IRAE and a biopsy should be considered.

Patients presenting with right upper-quadrant abdominal pain and/or unexplained nausea or vomiting should have LFTs performed immediately and reviewed before administering the next dose of study drug.

**Pancreas:** Symptoms of abdominal pain associated with elevations of amylase and lipase, suggestive of pancreatitis, may be associated with anti-CTLA-4 monoclonal antibody administration. The differential diagnosis of acute abdominal pain should include pancreatitis. Appropriate workup should include serum amylase and lipase tests.

Rev. 11/13

**Skin:** A dermatologist should evaluate persistent or severe rash or pruritus. A biopsy should be performed if appropriate and if possible, photos of the rash should also be obtained. Any non protocol drugs that could contribute to a drug reaction should be stopped if possible pending evaluation. Patients with low-grade ipilimumab-mediated skin toxicity (Grade 1 or 2) may remain on therapy and could be treated with symptomatic therapy (e.g., antihistamines). Low-grade symptoms persisting for 1 to 2 weeks and relapsing should be treated with topical or moderate dose oral corticosteroid therapy (e.g., prednisone 1 mg/kg once daily or equivalent). High-grade (Grade 3 or 4) symptoms require high-dose IV corticosteroid therapy (e.g., methylprednisolone 2 mg/kg once or twice per day or equivalent) to control initial symptoms. A skin biopsy should be performed if appropriate. Once rash or pruritus is controlled, the initiation of corticosteroid taper should be based on clinical judgment; however, the corticosteroid dose should be gradually tapered over a period of at least 1 month.

Patients with any high-grade skin related toxicity (Grade 3 regardless of causality) have to skip ipilimumab and may only continue treatment with ipilimumab if the initial symptoms have improved to  $\leq$  Grade 1, while patients with grade 4 skin toxicities have to permanently

Rev. 11/13

discontinue ipilimumab. Please see Sections [5.5.1.3](#), [5.5.1.5](#) and [Appendix XVIII](#).

**Eye:** An ophthalmologist should evaluate visual complaints with examination of the conjunctiva, anterior and posterior chambers and retina; visual field testing and an electroretinogram should also be performed. Patients with ipilimumab related uveitis or episcleritis have been treated with topical corticosteroid eye drops.

**Endocrine:** Subjects with unexplained symptoms such as fatigue, myalgias, impotence, mental status changes, or constipation should be investigated for the presence of thyroid, pituitary or adrenal endocrinopathies. An endocrinologist should be consulted if an endocrinopathy is suspected. If there are any signs of adrenal crisis such as severe dehydration, hypotension, or shock, intravenous corticosteroids with mineralocorticoid activity (e.g., methylprednisolone) should be initiated immediately. If the patient's symptoms are suggestive of an endocrinopathy but the patient is not in adrenal crisis, endocrine laboratory results should be evaluated before corticosteroid therapy is initiated.

Endocrine work up should include at least Thyroid stimulating hormone and free T4 levels to determine if thyroid abnormalities are present. TSH, prolactin and a morning cortisol level will help to differentiate primary adrenal insufficiency from primary pituitary insufficiency. Radiographic imaging (e.g., MRI) with pituitary cuts should be performed. If the pituitary scan and/or endocrine laboratory tests are abnormal suggestive of pituitary endocrinopathy, a short course of high dose corticosteroids (e.g., dexamethasone 4 mg every 6 hours or equivalent) should be strongly considered in an attempt to treat the presumed pituitary inflammation, but it is currently unknown if this will reverse the pituitary dysfunction. Abrupt discontinuation of corticosteroids should be avoided due to possible prolonged adrenal suppression. Once symptoms or laboratory abnormalities are controlled, and overall patient improvement is evident, the initiation of steroid taper should be based on clinical judgment; however the corticosteroid dose should be gradually tapered over a period of at least 1 month. Appropriate

hormone replacement therapy should be instituted if an endocrinopathy is documented, and it is possible that subjects may require life-long hormone replacement.

Patients diagnosed with hypophysitis should be permanently discontinued from additional ipilimumab therapy. Please see Sections [5.5.1.3](#), [5.5.1.5](#) and [Appendix XVI](#).

Rev. 11/13

Suspected irAEs should be documented in the patient's medical record.

---

**A Phase III Randomized Study of Adjuvant Ipilimumab Anti-CTLA4 Therapy Versus High Dose Interferon a-2b for Resected  
High risk Melanoma**

[figure not shown]
Rev. 9/14

**Appendix XIV  
GI Management Algorithms**

**PLEASE NOTE: THERE ARE TWO (2) SEPARATE E1609 GI MANAGEMENT ALGORITHMS. ONE IS TO BE USED FOR ARMS A AND D PATIENTS ONLY, AND THE OTHER FOR ARMS C AND F PATIENTS ONLY. PLEASE REFERENCE THE CORRECT VERSION OF THE ALGORITHM BASED ON THE ARM DESIGNATION OF THE PATIENT. THE ALGORITHMS APPEAR ON THE FOLLOWING 2 PAGES.**

## E1609 (Arms A and D) GI Management Algorithm

[figure not shown]

\*\* Patients on Arm A and Arm D with Grade 1 diarrhea/colitis must have ipilimumab held until resolution to Grade 0 (baseline) before resuming dosing with ipilimumab. Patients on Arm A and Arm D with Grade 2 diarrhea/colitis must have ipilimumab permanently discontinued.

Patients on IV steroids may be switched to oral corticosteroid (e.g., prednisone) at an equivalent dose at start of tapering or earlier, once sustained clinical improvement is observed. Lower bioavailability of oral corticosteroids should be taken into account when switching to the equivalent dose of PO corticosteroids. Ipilimumab may not be restarted while the patient is being treated with systemic corticosteroids except for patients on stable doses of hormone replacement therapy such as hydrocortisone.

**E1609 (Arms C and F) GI Management Algorithm**

\*\* Patients with Grade 2 colitis who require steroid therapy with resolution to ≤ Grade 1 severity must have a follow-up colonoscopy to document endoscopic (with or without pathologic) resolution of inflammation before resuming dosing with ipilimumab.

[figure not shown]
Patients on IV steroids may be switched to oral corticosteroid (e.g., prednisone) at an equivalent dose at start of tapering or earlier, once sustained clinical improvement is observed. Lower bioavailability of oral corticosteroids should be taken into account when switching to the equivalent dose of PO corticosteroids. Ipilimumab may not be restarted while the patient is being treated with systemic corticosteroids except for patients on stable doses of hormone replacement therapy such as hydrocortisone.

**A Phase III Randomized Study of Adjuvant Ipilimumab Anti-CTLA4 Therapy Versus High Dose Interferon a-2b for Resected High risk Melanoma**

**Appendix XV  
Hepatotoxicity Management Algorithms**

**E1609 (Arms A and D & C and F) Hepatotoxicity Management Algorithm**

Rev. 2/13, 11/13,  
9/14

\*Ipilimumab may be held/delayed rather than discontinued if AST/ALT  $\leq 5 \times$  ULN and Tbili  $\leq 3 \times$  ULN. Resume ipilimumab when AST/ALT/Tbili return to grade 1 and meet protocol specific retreatment criteria.

\*\*The recommended starting dose for grade 4 hepatitis is 2 mg/kg/day methylprednisolone IV.

[figure not shown]
Patients on IV steroids may be switched to oral corticosteroid (e.g., prednisone) at an equivalent dose at start of tapering or earlier, once sustained clinical improvement is observed. Lower bioavailability of oral corticosteroids should be taken into account when switching to the equivalent dose of PO corticosteroids. Ipilimumab may not be restarted while the patient is being treated with systemic corticosteroids except for patients on stable doses of hormone replacement therapy such as hydrocortisone.

**A Phase III Randomized Study of Adjuvant Ipilimumab Anti-CTLA4 Therapy Versus High Dose Interferon a-2b for Resected High risk Melanoma**

**Appendix XVI  
Endocrinopathy Management Algorithm**

**E1609 (Arms A and D & C and F) Endocrinopathy Management Algorithm**

Rev. 2/13, 11/13,  
9/14

Patients on IV steroids may be switched to oral corticosteroid (e.g., prednisone) at an equivalent dose at start of tapering or earlier, once sustained clinical improvement is observed. Lower bioavailability of oral corticosteroids should be taken into account when switching to the equivalent dose of PO corticosteroids. Ipilimumab may not be restarted while the patient is being treated with systemic corticosteroids except for patients on stable doses of hormone replacement therapy such as hydrocortisone.

---

[figure not shown]
**A Phase III Randomized Study of Adjuvant Ipilimumab Anti-CTLA4 Therapy Versus High Dose Interferon a-2b for Resected High risk Melanoma**

Rev. 9/14

**Appendix XVII  
Neuropathy Management Algorithms**

**PLEASE NOTE: THERE ARE TWO (2) SEPARATE E1609 NEUROPATHY MANAGEMENT ALGORITHMS. ONE IS TO BE USED FOR ARMS A AND D PATIENTS ONLY, AND THE OTHER FOR ARMS C AND F PATIENTS ONLY. PLEASE REFERENCE THE CORRECT VERSION OF THE ALGORITHM BASED ON THE ARM DESIGNATION OF THE PATIENT. THE ALGORITHMS APPEAR ON THE FOLLOWING 2 PAGES.**

[figure not shown]
## E1609 (Arms A and D) Neuropathy Management Algorithm

Patients on IV steroids may be switched to oral corticosteroid (e.g., prednisone) at an equivalent dose at start of tapering or earlier, once sustained clinical improvement is observed. Lower bioavailability of oral corticosteroids should be taken into account when switching to the equivalent dose of PO corticosteroids. Ipilimumab may not be restarted while the patient is being treated with systemic corticosteroids except for patients on stable doses of hormone replacement therapy such as hydrocortisone.

## E1609 (Arms C and F) Neuropathy Management Algorithm

[figure not shown]
Patients on IV steroids may be switched to oral corticosteroid (e.g., prednisone) at an equivalent dose at start of tapering or earlier, once sustained clinical improvement is observed. Lower bioavailability of oral corticosteroids should be taken into account when switching to the equivalent dose of PO corticosteroids. Ipilimumab may not be restarted while the patient is being treated with systemic corticosteroids except for patients on stable doses of hormone replacement therapy such as hydrocortisone.

**A Phase III Randomized Study of Adjuvant Ipilimumab Anti-CTLA4 Therapy Versus High Dose Interferon a-2b for Resected High risk Melanoma**

Rev. 9/14

**Appendix XVIII  
Skin Toxicity Algorithm**

**E1609 (Arms A and D & C and F) Skin Toxicity Algorithm**

Patients on IV steroids may be switched to oral corticosteroid (e.g., prednisone) at an equivalent dose at start of tapering or earlier, once sustained clinical improvement is observed. Lower bioavailability of oral corticosteroids should be taken into account when switching to the equivalent dose of PO corticosteroids. Ipilimumab may not be restarted while the patient is being treated with systemic corticosteroids except for patients on stable doses of hormone replacement therapy such as hydrocortisone.

---

## A Phase III Randomized Study of Adjuvant Ipilimumab Anti-CTLA4 Therapy Versus High Dose Interferon a-2b for Resected High risk Melanoma

### Appendix XIX Biomarkers of the Proinflammatory Response and Elements of Immune Suppression

Study PI: [name], PhD

#### **XIX.1 Hypotheses**

1. Based on significant preliminary data generated by our group and others we hypothesize that a baseline and /or early-on treatment prognostic biomarker signature in relation to ipilimumab and IFN $\alpha$  can be generated by assessing specific markers of the pro-inflammatory immune response and of immunosuppression in both tumor tissue and in circulating blood, when evaluated simultaneously due to the common systems biology.
  2. The prognostic biomarker signature generated will have therapeutic predictive value in relation to ipilimumab.
  3. Based on significant preliminary data we hypothesize that clustered genomic variants specific to patients who develop immune-related colitis after ipilimumab predict this toxicity.
- 

#### **XIX.2 Objectives**

1. Primary Objective: Generating prognostic biomarker signature for patients treated with Ipilimumab and high dose IFN $\alpha$  (HDI).
  - a. Aim 1: Testing of specific circulating biomarkers of therapeutically predictive value generated by significant preliminary data
    - i Cellular populations: (1) absolute lymphocyte count; (2) T regulatory (CD4+CD25hi+Foxp3+, CD4+CD25hi+CD39+) and MDSC (monocyte gate HLA-DR+ low/CD14+, monocyte gate Lin1-/HLA-DR-/CD33+/CD11b+, lymphoid gate Lin1-/HLA-DR-/CD33+/CD11b+); (3) IFN $\gamma$ +CD4+ and IFN $\gamma$ +CD8+ antigen specific T cells (gp-100, MART-1, NY-ESO-1 peptides); (4) CD4+ and CD8+ ICOS-hi T cells; (5) IFN $\gamma$ +CD8+CXCR3+VLA4+ T cells
    - ii Serum proteins: CRP, LDH, S100, MIA, YKL40, IL1 $\alpha$ , IL1 $\beta$ , IL2, IL2R $\alpha$ , IL6, IL8, IL10, IL17, IL12p40, TNF $\alpha$ , IFN $\alpha$ , MIP1 $\alpha$ , MIP1 $\beta$ , TNF-RII, TGF- $\alpha$ , TIMP-1, CXCL10 (IP10), CXCL11, CXCL9, VEGF
  - b. Aim 2: Testing of specific biomarkers within the tumor microenvironment (TME) of therapeutically predictive value generated by significant preliminary data
    - i Expression levels of immune related-genes (RNA microarray): CCL2, CCL3, CCL4, CCL5, CD8A, CXCL10, CXCL11, CXCL9, IDO, PRF1, GZMB, HLA-DMA, HLA-DOA, CD79B, IGH, IGKC, IGLC1, HLA-DQA1, IGHM, CD79A, IGHD, CD3G, CD3D, HLA-DPA1, LAT, VAV1, INPP5D, IL2RB, IGHG1, CIITA, IL21R, STAT1

- ii Tumor infiltrating lymphocytes and immunosuppressive markers (immunohistochemistry): CD3, CD4, CD8, FOXP3, PD-L1, IDO, CD45RO

Using known clinical covariates and the markers identified in Aims 1 and 2, we will use the entire data set to develop and validate models capable of identifying which patients belong to different prognostic groups.

2. Secondary Objectives:

- a. Testing the therapeutic predictive value in relation to ipilimumab of the prognostic biomarker signature identified in the primary objective.
- b. If a prognostic biomarker signature could not be generated based on the candidate biomarkers selected under the primary objective or if it fails to have a therapeutic predictive value, we will conduct a more comprehensive approach aimed at the generation and validation of a therapeutically predictive biomarker signature in relation to ipilimumab and HDI. This strategy will be feasible since we plan to conduct TME global RNA microarray studies that will generate global gene expression data. This testing approach will allow both global and individual gene expression data analysis.
- c. Testing the “immune-related colitis” predictive value of specific genomic variants generated by significant preliminary data.
- d. Testing for activating mutations (BRAF, NRAS) in patients without known tumor mutational status as tested in a CLIA certified laboratory.

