### **Power for Primary Objective: Prognostic Modeling**

Subjects will be divided into a training set and a validation set (250 each for the LIP and HIP groups, 300 for HDI group). Here we demonstrate our power in the development of a prognosis model in one of the ipilimumab arms. We base our power calculation on a test that compares the SN and SP simultaneously. Following the E1609 protocol, we expect that the cure rate for the ipilimumab arm will be 40% and the median RFS for the uncured patients is 0.48 years. As described above, we expect to obtain samples from  $\geq 80\%$  of the patients, after accounting for 95% assay success rate, we will have about 76 cases (patients who had event within 1 year) and 114 controls (patients who are followed up for 1 year without any event). We define a minimal useful model to be one with a sensitivity of 75% or higher and a specificity of 75% or higher. If the true sensitivity and specificity are 89% and 87% for our model, we will have over 80% power to claim that our model is significantly better than the minimal useful model ( $\alpha=0.05$ ).

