### XIX.9 Statistical Analysis Plan

- Statistical methods for the main analyses: For the single marker association with PFS and OS, Cox proportional hazards (CoxPH) regression will be used. Because some long-term cures have been observed in patients with stages IIB – III melanoma treated with HDI and ipilimumab, we will also perform exploratory analyses using a cure-rate model for RFS as a supplement to the CoxPH regression analyses proposed above. For multi-marker prognostic model, both the Lasso Cox proportional hazard regression and the Cox proportional hazard regression will be used. And the results will be compared.
- Transformations applied to variables: Distribution of data of different types will be checked and appropriate transformation will be used when necessary.
- Methods for marker cutpoint determination: For the predictive biomarker, we will follow the recommendation of Janes et al 2013 and use the marker-by-treatment predictiveness curves to guide the dichotomization of the marker (or risk score for multi-marker panel). Specifically, we will dichotomize the marker (or score) around the point where the two predictive curves cross.

- Variable selection procedures: We will use two strategies and compare our results: Cox proportional hazard regression with forward regression and Lasso Cox proportional hazard regression.
- List of standard clinical variables to be incorporated into models or other analyses: Clinical variables that we will consider to be included in the models are age, sex, Breslow thickness, recurrent disease at study entry, ulceration of the primary tumor, lymph-node status, number of positive lymph nodes, completion of lymph node dissection prior to treatment, microscopic extranodal extension, and mitotic rate in the primary tumor.
- Multiple-comparisons adjustment methods: To adjust for the multiple testing, the Benjamini and Hochberg's (BH) method will be used to control the false-discovery rate (FDR) at 5% for all candidate marker analyses. For the whole genome scan, we will use the procedure described in Storey 2002 to control the FDR at 5%.

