
groups (cutoff at the 33% and 67% percentiles of the score) will be calculated. The log rank test will be used to compare the RFS between the groups. The discrimination ability of the risk score on 1-year RFS will be assessed by time-dependent ROC analysis. *The same strategies will be used in the analysis of OS.*

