### Power Calculation for Predictive Modeling

The goal here is to determine whether there is a significant difference between the clinical benefits of patients in different marker strata. That is, we are testing the interaction of the dichotomized marker value (we discuss how to dichotomize the marker value in details in our analysis plan in the following section) and the treatment group. We calculate our power based on the method by Peterson and George.

We denote the hazard function for each patient subgroup as the following:

	Marker stratum 1	Marker stratum 2
HDI	$\lambda_{11} = \lambda(t)$	$\lambda_{12} = \lambda(t)\lambda_{\text{Marker}}(t)$
Ipilimumab	$\lambda_{21} = \lambda(t)\lambda_{\text{Ipi}}(t)$	$\lambda_{22} = \lambda_{\text{Ipi}}(t)\lambda_{\text{Marker}}(t)\lambda_{\text{Interaction}}(t)$

where

$\lambda(t)$  is the baseline hazard

$\lambda_{\text{Ipi}}(t)$  is the hazard for the Ipilimumab group

$\lambda_{\text{Marker}}(t)$  is the hazard for marker stratum2 and

$\lambda_{\text{Interaction}}(t)$  is the hazard for the treatment by marker stratum interaction.

Denote  $N$  the sample size,  $f_{ij}$ , the number of subjects in treatment group  $i$  and marker stratum  $j$ , and  $e_{ij}$ , the event probability in treatment group  $i$  and marker stratum  $j$ . Define that  $\Delta = \frac{\Delta_1}{\Delta_2} = \frac{\lambda_{11} / \lambda_{21}}{\lambda_{12} / \lambda_{22}}$ , then the power to test the null hypothesis of  $\Delta = 1$

can be calculated using the following formula:

$$\text{Power} = \Phi^{-1} \left( \sqrt{N(\log \Delta)^2 / \sum \frac{1}{e_{ij} f_{ij}}} - Z_{1-\alpha/2} \right)$$

- $\alpha = 0.01$  : we do not intend to validate more than 5 predictive markers (and/or panels) in the validation set, thus, our type I error is set at  $0.05/5=0.01$ . All tests will be two-sided.

- For the purpose of power calculation, we assume the RFS time follows an exponential distribution.
- N: 250 on the ipilimumab arm + 300 on the HDI arm. We expect that we will be able to obtain samples from approximately 80% of the subjects. We expect that the assay success rate is at least 95%. Thus N is estimated to be 418.

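### The planned validation of the Appendix XIX biomarker signature does not separate the markers' contribution from that of the clinical covariates

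*Combined protocol and SAP*

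**What the plan says.** Appendix XIX.2 gives as its primary objective a prognostic biomarker signature for patients treated with ipilimumab and HDI. It describes the model building thus: "Using known clinical covariates and the markers identified in Aims 1 and 2, we will use the entire data set to develop" and validate models that sort patients into prognostic groups. The list of standard clinical variables in XIX.9 reads "Clinical variables that we will consider to be included in the models are age, sex, Breslow thickness, recurrent disease at study entry", and goes on to ulceration, nodal factors and mitotic rate.

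The samples are split in half: "Subjects will be divided into a training set and a validation set (250 each for the LIP and HIP groups, 300 for HDI group". The Detailed Analysis Plan for the Primary Objective then validates the locked score in the held-out half. Hazard ratios are computed between score tertiles, "The log rank test will be used to compare the RFS between the groups", and 1-year discrimination is assessed by time-dependent ROC. McNemar tests compare the modelling algorithms with each other.

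The power section for the primary objective sets a fixed floor for a useful model, 75% sensitivity and 75% specificity, and powers a claim to exceed it.

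Separately, each marker is tested one at a time in a Cox model adjusted for known prognostic factors, with the false-discovery rate held at 5%. The plan states that this analysis does not select features for the multi-marker model.

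**The concern.** The conclusion the appendix wants is about circulating and tumor immune markers. The Detailed Analysis Plan itself calls the clinical variables known prognostic factors. If they are in the score, the score can separate risk groups with no help from the markers. A validated result could then be reported as a validated biomarker signature although the analysis never asked whether the markers add anything. A reader could not attribute the result to immune biology.

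**Working it through.** **1. What each planned analysis tests**

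| Planned analysis | What is tested | Isolates the markers? |
|---|---|---|
| Tertile hazard ratios and log-rank test | Whole score | No |
| Time-dependent ROC at 1 year | Whole score, no threshold stated | No |
| 75%/75% floor (power section) | Whole score against a fixed bar | No |
| McNemar tests | One algorithm against another | No |
| Adjusted single-marker Cox tests | One marker given clinical factors | Yes, per marker; not the signature |
| Screen before the machine-learning models | One marker, univariate | No |

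Appendix XIX contains no clinical-only model, nested test or change in AUC.

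**2. Reproducing the plan's power figure**

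Inputs: 250 per half for an ipilimumab arm; "We expect that we will be able to obtain samples from approximately 80% of the subjects"; "after accounting for 95% assay success rate". Then 250 × 0.80 × 0.95 = 190. The plan splits this 40%/60%: "we will have about 76 cases (patients who had event within 1 year) and 114 controls".

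Sidedness is not stated. I took a joint test with each part one-sided at 1 − √0.95 = 0.0253 (z = 1.954). Power for each part is Φ{[√n(p₁ − p₀) − z√(p₀(1 − p₀))] / √(p₁(1 − p₁))}.

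- Sensitivity, 0.89 against 0.75, n = 76: (1.220 − 0.846)/0.313 = 1.196, giving 0.884.
- Specificity, 0.87 against 0.75, n = 114: (1.281 − 0.846)/0.336 = 1.293, giving 0.902.
- Product: 0.884 × 0.902 = 0.798 (exact binomial 0.786).

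This agrees with the stated power of over 80% to within about 2 points.

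**3. Can a clinical-only score clear the 75%/75% floor?**

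The exact test needs at least 65 of 76 cases and 95 of 114 controls correctly classified. With equal sensitivity and specificity s and a normally distributed score, AUC = Φ(√2 · Φ⁻¹(s)).

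| s | AUC | Chance of clearing the floor |
|---|---|---|
| 0.70 | 0.77 | about 0% |
| 0.75 | 0.83 | 0.04% |
| 0.80 | 0.88 | 3% |
| 0.82 | 0.90 | 11% |
| 0.85 | 0.93 | 39% |

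**4. Can a clinical-only score pass the tertile log-rank test?**

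The documents give no clinical-only AUC, so it is an assumed range. The simulation uses 190 validation patients and a standard normal clinical score x with log hazard ratio b per SD. RFS follows the protocol's model, S(t) = [0.29 + 0.71·exp(−1.423t)] raised to the power 0.75·exp(bx − b²/4). Censoring is uniform between 1 and 4.3 years (12 months' minimum follow-up, 40 months' accrual). The test is a three-group log-rank test (2 df, 5%), with 1,500 runs per row. The score contains no marker information.

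| b | 1-year AUC of the score | Passes |
|---|---|---|
| 0 | 0.50 | 6% |
| 0.2 | 0.57 | 35% |
| 0.3 | 0.61 | 69% |
| 0.4 | 0.64 | 91% |
| 0.5 | 0.67 | 98% |

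Monte Carlo standard error is at most √(0.25/1500) = 1.3 points.

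**5. Sensitivity to estimating the score**

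Step 4 takes the clinical score as known. If it is fitted by Lasso Cox on 190 training patients together with pure-noise markers, the noise dilutes it and the pass rate falls. One such simulation (10 clinical covariates, 75 noise markers) gave 19%, 74% and 97% at clinical-only AUCs of 0.56, 0.66 and 0.74. A test of the marker score given the clinical score passed in 0–2% of the same trials. These rates depend on simulation choices, so I use them for direction only.

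**The case against.** The strongest reply is the 75%/75% floor. It is the only success benchmark the appendix states, and step 3 shows that a clinical score of ordinary strength would fail it. That stands as far as it goes. A reader might infer from step 4 that log-rank significance is the plan's criterion for a validated signature. The documents do not say so; no passage sets that criterion. Equally, the validation paragraphs do not restate the floor as a decision rule. Clearing it would in any case show that the whole score is good, not why.

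Second, the clinical content of the final model is not settled. XIX.9 says only that clinical variables will be considered, and the model-development paragraphs speak of markers within and across Aims. So it goes too far to say that every validated model will contain clinical covariates. XIX.2 does put them in the primary-objective models. A marker-only score would still need an added-value test, because markers can stand in for stage or tumor burden.

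Third, the adjusted single-marker tests would be reported alongside the signature and give real evidence on individual markers. They do not test the signature.

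Fourth, one might infer that a clinical-plus-noise signature would pass unchecked into the predictive objective, 2(a). It would not. A risk score goes forward there only with a significant qualitative treatment interaction in a covariate-adjusted model, re-tested in held-out data at p < 0.01. Being prognostic gives it no advantage.

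**Conclusion.** The concern holds in a limited form. The planned validation cannot distinguish a signature in which the markers add prognostic information from one in which they add none. If clinical factors alone reach a 1-year AUC of 0.61 to 0.67, a score with no marker information passes the tertile log-rank test about 69% to 98% of the time. Those rates assume markers that add nothing, a known clinical score, the protocol's RFS model and an AUC range the documents do not supply; an estimated score diluted by noise markers would pass less often. If the 75%/75% floor were enforced, such a score would almost never succeed below an AUC of about 0.83, and would exceed 10% only near 0.90.

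The documents do not support saying that the markers are noise or that a false signature is likely to be declared. XIX.4 reports S100B, a candidate marker, as an independent predictor of OS after adjustment for prognostic factors. The point is that the validation as written could not settle the question. It is worth correcting, but only within the correlative appendix; the trial's RFS and OS analyses are unaffected.

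**What to change.** In the model-development and validation paragraphs of the Detailed Analysis Plan:

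- State which clinical variables enter the final models.
- Fit a clinical-only Cox model for each arm in the same training set and lock it with the combined model.
- In the validation set, fit a Cox model with the locked clinical score and the locked marker score, and test the marker score (one degree of freedom, level fixed in advance). Report the change in 1-year AUC from clinical-only to combined, with a confidence interval.
- Require that test before concluding that the markers add prognostic information.
- Keep the combined model and the 75%/75% benchmark for risk grouping, and say whether the benchmark is a decision rule.

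The test holds its level when the markers add nothing, to the extent that the locked clinical score captures the clinical information. The cost is wording in XIX.9 and one extra model per arm, on clinical variables the plan already lists for modelling; no new samples are needed. The downside is a stricter and possibly less favourable result.
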